5.4.2 Bone Age

Bone age SDS will be calculated as (bone age – chronological age) / standard deviation) where the chronological age is the age in months at the time of the X-ray evaluation and the standard deviation is the sex- and age-specific standard deviation, as defined in the table below:

Table 5-5	Variability in Bone Age			
Chronologic Age in Months	Boys Standard Deviation	Girls Standard Deviation		
12	2.1	2.7		
18	2.7	3.4		
24	4	4		
30	5.4	4.8		
36	6	5.6		
42	6.6	5.5		
48	7	7.2		
54	7.8	8		
60	8.4	8.6		
66	9.1	8.9		
72	9.3	9		
84	10.1	8.3		
96	10.8	8.8		
108	11	9.3		
120	11.4	10.8		
132	10.5	12.3		
144	10.4	14		
156	11.1	14.6		
168	12	12.6		
180	14	11.2		
192	15	15		
204	15.4	15.4		

If the chronologic age falls between two values in the table above, the closest age should be used. If the chronologic age falls exactly in the middle between 2 values in the table above, then the age above the chronologic age should be used.

Table 5-6Time windows for bone data

Planned assessment	Time window	
Baseline	Days ≤1	
Month 6 (Day 168)	Days 85 – 252	
Month 12 (Day 336)	Days 253 – 420	
Month 18 (Day 504)	Days 421 – 588	
Month xx (Day xx * 28)	Days ((xx – 3) * 28 + 1) – Day ((xx + 3) * 28)	
End of Treatment (EoT)	Earliest data available on or after EoT date up to and including 30 days after EoT	
Day 1 = date of first intake of study drug		
xx = Every 12 months		

5.5 Statistical models

5.5.1 Primary analysis

Responses will be summarized in terms of percentage rates with 95% and 80% CIs. An exact binomial CI (implemented using SAS procedure FREQ with EXACT statement for one-way tables) will be calculated [Clopper CJ and Pearson ES. (1934) The use of confidence or fiducial limits illustrated in the case of the binomial. Biometrical, 26, 404-413].

SAS procedure FREQ will be used to estimate the proportion of responders (binary outcome = 1 or "Yes"), along with the associated 95% (= $100 \times (1 - two-sided \ alpha \ level$)) two-sided Pearson-Clopper CI.

When there are no responders, SAS does not produce a CI by default. To obtain a CI in this situation, PROC FREQ is used by changing **level** = "No". From the results of this modified procedure, the values in percent of the LCL and UCL of a 0% response rate are calculated as follows:

$$LCL_{LEVEL="Yes"} (\%) = 100\% - UCL_{LEVEL="No"} (\%)$$

 $UCL_{LEVEL="Yes"} (\%) = 100\% - LCL_{LEVEL="No"} (\%)$

Multiplicity adjustment

Not applicable.

5.5.2 Key secondary analysis

Not applicable.

5.5.3 Secondary efficacy analysis

To analyze time to event endpoints (TTR, DOR, PFS and OS). An estimate of the survival function will be constructed using Kaplan-Meier (product-limit) method as implemented in PROC LIFETEST with METHOD=KM option. The PROC LIFETEST statement will use the option CONFTYPE=LOGLOG. The TIME statement will include a variable with survival times and a (right) censoring variable with a value of 1, representing censoring. Kaplan-Meier survival and failure function estimates from this procedure will be used to construct the Kaplan-Meier figures.

Median survival will be obtained along with 95% CI calculated from PROC LIFETEST output using the method of [Baumgartner RN, Roche AF, Himes (1986). Incremental growth tables: supplementary to previously published charts. American Journal of Clinical Nutrition, 43, 711-22.

Brookmeyer R and Crowley J. (1982)]. Kaplan-Meier estimates of the survival function with 95% CI at specific time points will be summarized. The standard error of the Kaplan-Meier estimate will be calculated using Greenwood's formula [Collet D (1994).].

5.5.4 Implementation of RANO guidelines (protocol Appendix 3)

As described in the protocol, the ORR will be evaluated by RANO criteria for solid tumors. This section provides some details on how to derive these endpoints by RANO and further details are included in the protocol Appendix 3.

The RANO criteria for assessment of LGG differs from that for HGG primarily in that LGG assessments utilize T2/FLAIR imaging while HGG assessments utilize Gadolinium enhanced imaging.

The major differences between RECIST 1.1 and RANO include:

- The measurability criteria for target lesion by RANO is based on two dimensions i.e two perpendicular diameters are measured for each target lesion;
- Corticosteroids use and clinical status are also considered for determining overall response;
- There are two types of non-target lesions by RANO: T1 enhancing non-target lesions and lesions on T2/FLAIR. Both types of non-target lesions contribute to the non-target lesion response.

Overall Lesion Response Collected on RANO eCRF page

In this study, Independent reviewer reported overall response and Investigator reported overall lesion response will be used for primary and secondary endpoints.For investigator, the overall response by RANO will be derived based on the collected overall lesion response on eCRF page "RANO Overall Lesion Response" (ZR domain, ZRCAT = "RESPONSE ASSESSMENT IN NEURO-ONCOLOGY", and ZRSCAT = "OVERALL LESION RESPONSE").

For independent reviewer, the overall response by RANO will be derived based on the collected overall lesion response on eCRF page "RANO Overall Lesion Response" (ZR domain, ZRCAT = "RESPONSE ASSESSMENT IN NEURO-ONCOLOGY", and ZRSCAT = "OVERALL RESPONSE").

There will be two evaluations at a given assessment for independent reviewer i.e. primary RANO radiologic review without clinical data (read 1 – ZREVAL = "PRIMARY REVIEW") and a secondary RANO review with clinical data (read 2 – ZREVAL = "SECONDARY REVIEW"). Secondary RANO review (read 2) with clinical data will be used for the primary endpoint of Best overall response per independent review. Primary review (read 1) will be used in supportive analyses based on radiographic review only, without clinical data.

Calculation of Overall Lesion Response by RANO

Overall lesion responses by RANO are also calculated from the following components:

- 1. Target lesion measurements;
- 2. Non-target lesion response;
- 3. New lesion present (Yes/No);
- 4. Corticosteroids use;
- 5. Clinical status.

All these components are collected on the following eCRF pages for investigator:

- RANO target lesion Measurable enhancing lesion (T1) (ZI domain, ZICAT = "MODIFIED RANO CRITERIA FOR BRAIN METASTASES", ZISCAT = "TARGET ENHANCING T1");
- RANO non-target lesion Non-measurable enhancing lesion (T1) (ZI domain, ZICAT = "MODIFIED RANO CRITERIA FOR BRAIN METASTASES", ZISCAT = "NON-TARGET ENHANCING T1");
- 3. RANO non-target lesion Non-enhancing lesion (T2/FLAIR) (ZI domain, ZICAT = "MODIFIED RANO CRITERIA FOR BRAIN METASTASES", ZISCAT = "NON-TARGET NON ENHANCING T2/FLAIR");
- 4. RANO New Lesion (ZI domain, ZICAT = "MODIFIED RANO CRITERIA FOR BRAIN METASTASES", ZISCAT = "NEW");
- 5. Corticosteroids use and clinical status are collected on the Modified RANO Assessment (ZR domain, ZRCAT = "MODIFIED RANO CRITERIA FOR BRAIN METASTASES", ZISCAT = "RESPONSE ASSESSMENT").

All the above components are collected on the same eCRF pages for independent reviewer with the exception of ZICAT = " RESPONSE ASSESSMENT IN NEURO-ONCOLOGY".

Each target lesion by RANO criteria has two perpendicular diameters collected. In order to calculate the target lesion response, the product of the two perpendicular diameters is calculated for each target lesion. Then the sum of the products of diameters of all target lesions is compared to the baseline or nadir to determine the target lesion response.

The non-target lesion response is collected on the field of "Non-target lesion present" in the Modified RANO Assessment page, and is evaluated based on both non-target lesion eCRF pages as shown above.

The RANO response/progression criteria are summarized in Table 5-7.

	CR	PR	SD	PD
T1-enhancing disease	None	≥50% decrease from baseline	<50% decrease from baseline but <25% increase from nadir	≥25% increase from nadir*
T2/FLAIR	Stable or improved	Stable or improved	Stable or improved	Unequivocal PD*
New Lesions	None	None	None	Present*
Corticosteroids	None	Stable or decreased	Stable or decreased	NA**
Clinical Status	Stable or improved	Stable or improved	Stable or improved	Worsened*
Requirement for Response	All	All	All	Any*

Table 5-7 Summary of the RANO response criteria

CR=complete response; PR=partial response; SD=stable disease; PD=progressive disease *: Progression occurs when this criterion is met

**: Not Applicable (NA): Increase in corticosteroids alone will not be taken into account in determining progression in the absence of persistent clinical deterioration

5.6 Estimands

5.6.1 Primary estimand for the primary objective

The primary clinical question of interest is: what is the ORR by independent review as per RANO criteria for the combination treatment of dabrafenib + trametinib in children and adolescent subjects with BRAFV600 mutant relapsed or refractory HGG, regardless of study treatment discontinuation and before start of any new anti-neoplastic therapy.

The justification for the primary estimand is that it will capture the treatment effect of the study drug even after treatment is discontinued, but avoid potential confounding effects of any other new anti-neoplastic therapy.

The primary estimand is characterized by the following attributes:

- 1. Population: all subjects treated with BRAFV600 mutant relapsed or refractory HGG. Further details on the population are provided in protocol Section 5.
- 2. Primary Variable: BOR by independent review as per RANO criteria.

3. Treatment: dabrafenib plus trametinib, regardless of treatment discontinuation. Handling of intercurrent events:

- **Discontinuation of study treatment for any reason:** Per treatment policy strategy, tumor assessment data collected after discontinuation of study treatment for any reason will be used to derive BOR.
- **Start of new anti-neoplastic therapy**: Per while on treatment strategy, tumor assessments collected before start of new anti-neoplastic therapy will be used to derive BOR. Tumor assessments collected on/after the start of new therapy will not be considered for evaluation of BOR.

Novartis	Confidential	Page 56
SAP Final Analysis HGG		CDRB436G2201

Summary measure: proportion of subjects with BOR of a confirmed CR or PR by independent review as per RANO criteria. See section 2.5.2 for details.

Sensitivity analyses for primary endpoint/estimand will be performed using the evaluable set, with all other aspects of the estimand as defined above. Additionally, analyses with response as assessed by the investigator (instead of by central review) will be done under the same estimand attributes.

5.6.2 Handling of missing values not related to intercurrent event

Subjects in FAS with unknown or missing BOR will be noted as such in the appropriate tables/listings and counted as non-responders in the analysis of ORR. If there is no baseline tumor assessment, all post-baseline overall lesion responses are expected to be "Unknown". If no valid post-baseline tumor assessments are available, the BOR must be "unknown" unless progression is reported.

For the purpose of primary analysis, subjects with a BOR of "unknown" (UNK) will be treated as non-responders in estimating the ORR in the FAS.

5.6.3 Supplementary analysis

A supplementary analysis for the primary estimand will be done as defined below:

- 1. Population: all subjects treated with BRAFV600 mutant relapsed or refractory HGG. Further details on the population are provided in protocol Section 5.
- 2. Treatment: dabrafenib plus trametinib, regardless of treatment discontinuation or start of new anti-neoplastic therapy.
- 3. Variable: BOR by independent review as per RANO criteria.

Handling of intercurrent events:

- **Discontinuation of study treatment for any reason** Per treatment policy strategy, tumor assessment data collected after discontinuation of study treatment for any reason other than PD will be used to derive BOR.
- **Start of new anti-neoplastic therapy-** Per treatment policy strategy, tumor assessment data collected after start of anti-neoplastic therapy will be used to derive BOR.

Summary measure: proportion of subjects with BOR of a confirmed CR or PR by independent review as per RANO criteria.

6 Reference

- 4. American Academy of Pediatrics. (2004) The fourth report on the diagnosis, evaluation, and treatment of high blood pressure in children and adolescents. Pediatrics, 114, 555-76.
- 6. Brookmeyer R and Crowley J. (1982) A Confidence Interval for the Median Survival Time. Biometrics, 38, 29 41.

- 7. Clopper CJ and Pearson ES. (1934) The use of confidence or fiducial limits illustrated in the case of the binomial. Biometrical, 26, 404-413.
- 8. Collet D (1994). Modelling survival data in medical research. London, Chapman & Hall.
- 11. Kalbfleisch JD and Prentice RL. (2002) The Statistical Analysis of Failure Time Data. Wiley Series in Probability and Statistics.

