2.3.1 Patient disposition

The number (%) of patients in the FAS who completed treatment, who discontinued the study phases and the reason for discontinuation will be presented.

The following summaries will be provided: % based on the total number of FAS patients:

- Number (%) of patients who were treated (based on 'DAR' eCRF pages of each study treatment component completed with non-zero dose administered);
- Number (%) of patients who completed the study treatment phase (based on the 'End of Treatment Disposition' page)
- Number (%) of patients who discontinued the study treatment phase (based on the 'End of Treatment Disposition' page)
- Primary reason for study treatment phase discontinuation (based on the 'End of Treatment Disposition' page)
- Number (%) of patients who have entered the post-treatment follow-up (based on the 'End of Treatment Disposition' page);

- Number (%) of patients who have discontinued from the post-treatment follow-up (based on the 'End of Post Treatment Phase Disposition' page);
- Reasons for discontinuation from the post-treatment follow-up (based on 'End of Post Treatment Phase Disposition' page);
- Number (%) of patients who have entered the survival follow-up (based on the 'End of Treatment Disposition' or 'End of Post Treatment Phase Disposition' page).
- Number (%) of patients who have rolled over to long-term follow-up study G2401. (based on the 'EOT_Rollover' disposition page).

Protocol deviations

The number (%) of patients in the FAS with any protocol deviation will be tabulated by deviation category (as specified in the study Data Handling Plan). All protocol deviations will be listed.

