2.5 Analysis of the primary objective

The primary objective is to demonstrate the antitumor activity of dabrafenib in combination with trametinib as measured by ORR to study treatment by central independent review assessment using RANO criteria, in children and adolescent patients with BRAF V600 mutation positive relapsed or refractory HGG.

2.5.1 **Primary endpoint**

ORR is defined as the proportion of patients with best overall response (BOR) of confirmed complete response (CR) or partial response (PR) according to RANO criteria (see Appendix 3 of the study protocol). ORR will be calculated based on the FAS using central independent review of tumor assessment data. Only tumor assessments performed before the start of any further antineoplastic therapy (i.e. any additional secondary antineoplastic therapy or surgery) will be considered in the assessment of BOR. See Section 5.6 for primary estimand definition.

Best overall response

The BOR will be assessed based on reported responses across all evaluation time points. Both CR and PR must be confirmed by repeat assessments performed not less than 4 weeks after the criteria for response are first met. The next scheduled assessment may be used for purposes of

confirmation of response. In the absence of a confirming scan 4 weeks later, this response will be considered only stable disease (SD).

BOR for each patient is determined from the sequence of overall responses according to the following rules, up to progression:

- CR = at least two determinations of CR at least 4 weeks apart before progression
- PR = at least two determinations of PR or better at least 4 weeks apart before progression (and not qualifying for a CR)
- SD = requires at least one SD assessment (or better) determined at or beyond the second regularly scheduled tumor assessment (nominally week 16 i.e >= 105 days allowing for the ±1 week visit window) after start of study treatment (and not qualifying for CR or PR).
- PD = progression after start of study treatment (and not qualifying for CR, PR or SD).
- UNK = all other cases (i.e. not qualifying for confirmed CR or PR and without SD at or beyond the second regularly scheduled post-baseline tumor assessment or progression)

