2.5.3 Supportive analyses

As sensitivity analysis, ORR will be calculated and summarized for patients from the Evaluable Set. ORR will be summarized using descriptive statistics (N, %) along with two-sided exact binomial 95% and 80% CIs [Clopper CJ and Pearson ES. (1934) The use of confidence or fiducial limits illustrated in the case of the binomial. Biometrical, 26, 404-413].

New anticancer therapy sensitivity analysis for ORR

The analyses of ORR will be repeated using a stricter ITT approach i.e. including all response assessments irrespective of new anti-neoplastic therapy using the FAS. This analysis will only be performed if data permits.

Novartis	Confidential	Page 25
SAP Final Analysis HGG		CDRB436G2201

Response evaluations recorded after the initiation of new anti-neoplastic therapy will be included in sensitivity analysis of ORR, (i.e. the occurrence of new anti-neoplastic therapy will be ignored for the analyses). The sensitivity analyses will be performed based on both the investigator and independent review assessments using the FAS. In the summary tables, this approach is referred as 'new anticancer therapy ORR sensitivity analysis'.

Concordance analysis of ORR

An assessment of the concordance between central independent reviewer assessment and local investigator assessment of the BOR for each patient will be provided. The calculation will be based on the percent agreement (the proportion of response outcomes that agree or match across both independent reviewer and investigator assessments).

Reasons for "Unknown" BOR

Patients with 'unknown' BOR will be summarized by reason for having unknown status. The following reasons will be used:

- No valid post-baseline assessment
- All post-baseline assessments have overall lesion response UNK
- New anti-neoplastic therapy started before first post-baseline assessment
- SD and/or unconfirmed CR/PR only occurring prior to week 16 visit

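### The HGG supplementary ORR estimand (final SAP 5.6.3) is labelled treatment policy but excludes scans after discontinuation for PD, so it no longer differs from the primary estimand only in the handling of new therapy

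*SAP*

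**What the plan says.** All references are to the HGG final SAP unless stated.

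- **Supplementary estimand, 5.6.3.** The treatment attribute is "dabrafenib plus trametinib, regardless of treatment discontinuation or start of new anti-neoplastic therapy". The first intercurrent-event bullet is headed as covering discontinuation for any reason and is called treatment policy. Its rule is that "tumor assessment data collected after discontinuation of study treatment for any reason other than PD will be used to derive BOR". The second bullet, on new therapy, reads "Per treatment policy strategy, tumor assessment data collected after start of anti-neoplastic therapy will be used to derive BOR" and has no PD exception.
- **Primary estimand, 5.6.1.** For discontinuation: "tumor assessment data collected after discontinuation of study treatment for any reason will be used to derive BOR". For new therapy: "Tumor assessments collected on/after the start of new therapy will not be considered for evaluation of BOR".
- **New-therapy sensitivity analysis, 2.5.3.** ORR is repeated "including all response assessments irrespective of new anti-neoplastic therapy using the FAS", if data permit, for both the investigator and the independent review.
- **Derivation of BOR, 2.5.1.** "BOR for each patient is determined from the sequence of overall responses according to the following rules, up to progression".
- **LGG final SAP, 5.6.3.** The parallel supplementary estimand uses scans after discontinuation for any reason and has no PD exception.

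The exception also stands in section 5.5.3 of HGG SAP Amendment 2, so it was carried forward. Neither document gives a reason for it.

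**The concern.** A treatment policy strategy uses the data whether or not the event happens. A rule that discards data after one class of discontinuation is not treatment policy for that class. The first bullet of 5.6.3 therefore contradicts its own heading, its strategy label and the treatment attribute above it.

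A supplementary estimand placed beside the primary is useful when it changes one thing. Here that should be the handling of new anti-neoplastic therapy. As written, two rules change, in opposite directions: scans after new therapy are added, and scans after discontinuation for PD are removed. If the two ORRs differ, the difference cannot be assigned to new therapy alone. If they agree, the agreement may come from two changes that offset each other.

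There is also a programming problem. For a patient who stops for PD and then starts new therapy, the first bullet of 5.6.3 excludes the later scans and the second includes them. The SAP does not say which bullet governs.

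**Working it through.** No sample size, power or alpha figure is at issue, so the check compares the rules and then applies them to constructed patients.

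**Step 1. When can the exception change a result?** BOR is cut at progression (2.5.1). The variable in 5.6.3 is BOR by independent review, so scans after central PD count under no rule. The reason for stopping treatment, however, is taken from the End of Treatment disposition page (2.3.1), not from the central read. The SAP allows the two to disagree. Section 2.7.1 foresees discontinuation for progression without RANO evidence. Section 1.1 continues scans in patients who stop without RANO progression until centrally confirmed progression or death, even after new therapy. The exception therefore matters only when three things hold together: the recorded reason is PD, there is no central PD, and later scans exist.

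**Step 2. Constructed sequences.** Central reads are given by week. A response needs two PR or CR reads at least 4 weeks apart before central PD. PD in the first bullet of 5.6.3 is read as the disposition reason, and that bullet is taken to govern.

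| Case | Central reads | Stop | New therapy | Primary 5.6.1 | 5.6.3 as written | 2.5.3 |
|---|---|---|---|---|---|---|
| A | SD 8, PD 16, PR 24, PR 32 | wk 16, PD | wk 18 | no | no | no |
| B | SD 8, PR 16, PR 24 | wk 17, PD | none | yes | **no** | yes |
| C | SD 8, SD 16, PR 24, PR 32 | wk 17, PD | wk 18 | no | **no** | yes |
| D | SD 8, SD 16, PR 24, PR 32 | wk 17, AE | wk 18 | no | yes | yes |
| E | SD 8, PR 16, PR 24 | wk 17, AE | none | yes | yes | yes |

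- A: once central PD is recorded, the exception has no effect.
- B: the confirming scan at week 24 is dropped. A primary responder becomes a supplementary non-responder, with no new therapy involved.
- C: scans after new therapy that 2.5.3 keeps are dropped. If the second bullet of 5.6.3 governed instead, C would be a responder, so the result depends on a priority the SAP does not state.
- D and E: patients who stopped for another reason are handled as intended.

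**Step 3. After deletion of 'other than PD'.** The 5.6.3 column equals the 2.5.3 column in all five cases, and every primary responder is also a supplementary responder.

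**Step 4. Scale.** With about 40 patients (1.1), one reclassified patient moves ORR by 1/40 = 2.5 points. For example, 14/40 = 35.0% (exact 95% CI 20.6 to 51.7) becomes 15/40 = 37.5% (22.7 to 54.2). Both intervals reproduce Table 3-1 of HGG SAP Amendment 2.

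**The case against.** The strongest reply is that 'PD' in 5.6.3 may mean progression on the independent review itself. The phrase would then only repeat the cut-off in 2.5.1 and no result would change. The SAP does not say which meaning applies, so this reading is possible. It leaves the contradiction with the heading and the strategy label in place, and it makes the three words redundant.

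Second, the affected group may be very small. Section 1.1 provides continued scans for patients who stop without RANO progression. It does not clearly extend this to patients stopped for investigator-assessed RANO progression. Such a patient would also have to lack a confirmed response before stopping and gain one only through later scans. This stands: the count may be zero.

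Third, 2.5.3 already plans a repeat of ORR that ignores new therapy on central review in the FAS. If data permit, a reader gets the one-change comparison there. This reduces the harm but leaves two central-review analyses with different stated rules.

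A reader might go further and infer that 5.6.3 leaves out the very patients it was designed for. The document does not support that. It nowhere says the analysis targets patients who stopped for PD, no patient leaves the FAS, and patients who switch therapy after stopping for another reason still contribute (case D). Nor does the SAP say that 5.6.3 and 2.5.3 are one analysis: they have a similar purpose but different names, and 2.5.3 also covers the investigator review.

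**Conclusion.** The point holds as an internal contradiction with a narrow consequence. The exception in 5.6.3 disagrees with its own label and treatment attribute, with the bullet that follows it, with 5.6.1, with 2.5.3 and with the LGG final SAP. Where it bites, a confirmed response can count in the primary ORR and not in the supplementary ORR, so the supplementary figure can fall below the primary for a reason unrelated to new therapy.

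This rests on two assumptions: that PD in 5.6.3 means the recorded discontinuation reason, and that the cut-off in 2.5.1 applies to the supplementary BOR as well. The size is about 2.5 points of ORR per reclassified patient. Any statement of how many patients are affected would be a guess, because the SAP gives no count. The primary ORR does not change, and section 2.5.2 makes the final analysis descriptive with no hypothesis test. The wording should be corrected, but it does not threaten the trial's main result.

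**What to change.** Delete 'other than PD' from the first intercurrent-event bullet of 5.6.3 in the HGG final SAP. The supplementary estimand then differs from the primary only in the handling of new anti-neoplastic therapy and agrees with 2.5.3 and the LGG final SAP. The conflict between its two bullets also disappears.

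If the exception is intended, the SAP should give the reason, stop calling the strategy treatment policy for that event, say whether PD means the disposition reason or central RANO PD, and say which bullet governs when a patient stops for PD and then switches.

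The cost is three words and the matching line in the programming specification. No new data are needed. The same words in Amendment 2 need no separate action for the final analysis, which the final SAP governs.
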